8.1.3 Follow up period

8.1.3.1 Visit 9 / Day 113, Week 16 (+/- 5 days)

The Investigator or designee will:

1. Collect information regarding AE (including review of laboratory values) and concomitant therapies/procedures.
2. Perform vital signs measurements.
3. Complete urine pregnancy test for female of childbearing potential only.
4. Conduct respiratory medical assessments, including PEF for subjects with a history of asthma.
5. Collect blood samples for PK, ADA
6. Control the good healing of biopsies when applicable.
7. Check subject's record for pruritus NRS and VRS and remind subject to complete them daily
8. Schedule the next visit for Visit 10.

8.1.3.2 *Visit 10 / Day 126, Week 18 (+/- 7 days)*

The Investigator or designee will:

1. Collect information regarding AE (including review of laboratory values) and concomitant therapies/procedures.
2. Check subject's record for pruritus NRS and VRS.
3. Perform physical examination & vital signs measurements.
4. Complete urine pregnancy test for female of childbearing potential only.
5. Conduct respiratory medical assessments, including PEF for subjects with a history of asthma.
6. Complete the evaluation of PAS and IGA.
7. Collect blood samples for PK, ADA
8. Take whole body photographs (selected centers only).
9. Collect the device used for Pruritus assessments
10. Complete the exit form.

8.1.4 *Early Termination visit or unscheduled visit:*

The Investigator or designee will:

1. Collect information regarding AE (including review of laboratory values) and concomitant therapies/procedures.
2. Check subject's record for pruritus NRS and VRS.
3. Ask subject to complete the DLQI.

4. Complete the evaluation of PAS and IGA.
5. Perform physical examination & vital signs measurements and ECG.
6. Conduct respiratory medical assessments, including PEF for subjects with a history of asthma.
7. Complete urinalysis.
8. Complete urine pregnancy test for female of childbearing potential only.
9. Collect blood samples for hematology & biochemistry
10. Collect blood samples for PK and ADA.
11. Complete the exit form in case of early termination and collect e-devices.

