## 4.2 Efficacy and Safety Variables

### 4.2.1 Efficacy Variables

#### 4.2.1.1 Pruritus Numeric Rating Scale (NRS)

Pruritus NRS is a scale to be used by the subjects to report the intensity of their pruritus (itch) during the last 24 hours all along the study from first screening visit to the follow-up visit. Subjects will receive instructions on how to record their pruritus NRS scores on an electronic device and will complete the assessment once daily at home in the evening throughout the clinical trial (including the follow-up period).

Subjects will be asked the following questions in their local language:

- For average itch intensity: “On a scale of 0 to 10, with 0 being ‘no itch’ and 10 being ‘worst itch imaginable’, how would you rate your itch overall during the previous 24 hours?”
- For maximum (Peak) itch intensity: “On a scale of 0 to 10, with 0 being ‘no itch’ and 10 being ‘worst itch imaginable’, how would you rate your itch at the worst moment during the previous 24 hours?”

Weekly prorated average score will be calculated and used in the analysis. If a subject has less than 5 diary entries in a week, the weekly average scores will be set to missing. Refer to Section 5.2 for classification of diary data into analysis week/visit.

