**Analysis Visit**

Study day is relative to date of randomization. Day -1 is the day before randomization, and day 1 is date of randomization.

Assessments at early termination and unscheduled visits will be slotted based on the following visit window.

Period	Analysis Visit	Target day (relative to randomization)	Day ranges
Screening Period	Screening 1	-28	-28 to -8
	Screening 2	-7	-7 to -1
Treatment	Baseline	1	≤1
	Week 1	8	2-11
	Week 2	15	12-22
	Week 4	29	23-43
	Week 8	57	44-71
	Week 12	85	72-99
Follow-up	Week 16	113	100-119
	Week 18	126	>119

The diary reported during study will be classified into analysis visits as follows (i.e., during the 7 days prior to the target day of analysis visit. In this case, the target day of analysis visit is relative to date of the first planned study drug.):

- Day -7 to -1 = Baseline
- Day 1 to 7 = Week 1
- Day 8 to 14 = Week 2
- Day 22 to 28 = Week 4
- Day 50 to 56 = Week 8
- Day 78 to 84 = Week 12
- Day 106 to 112 = Week 16
- Day 120 to 126 = Week 18

These analysis visits will be used in the calculations for all week-based parameters collected on subject's diary (e.g., pruritus NRS, VRS, Sleep disturbance NRS, PAS, DPS, DLQI) Other non-diary data, such as , IGA, vital signs, body weight, clinical laboratory assessments, respiratory assessment/PEF, will be analyzed according to actual scheduled visits.

For efficacy and safety data (except clinical laboratory assessments), where two or more assessments (include both scheduled and unscheduled assessments) are available for the same visit interval, the one closest to the target visit date will be used for the summary and analyses. For clinical laboratory assessments, if repeated measurements are taken for either time point (scheduled visit), then the last measurement will be used for the value for that time point. Unscheduled labs will be included in listings, but not summaries of the data. All post baseline assessments, including repeated or unscheduled visits, will be used for potentially clinically significant value (PCSV) determinations.

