(e) Only for female of childbearing potential. Serum pregnancy test to be performed at screening visit 1 and urine pregnancy test (UPT) for all other visits. UPT should have a sensitivity threshold of less than 25mIU/mL. There should be at least 14 days between the serum pregnancy test at screening and the UPT at baseline.

(f) Respiratory assessments for all subjects, but PEF will be measured only for subjects with medical history of asthma

Study period Visit Week Day Visit window	Screening period (Day -28 to Day-1)		Treatment period							Observation period/ Follow up		Early termination (E/T) or Unscheduled visit (if applicable)
	V1 Screening 1 D-28 to D-8	V2 screening 2 Day-7 (a) Day 1	V3 Baseline Day 1 ±1 day	V4 W1 Day 8 ±2 days	V5 W2 Day 15 ±2 days	V6 W4 Day 29 ±2 days	V7 W8 Day 57 ±2 days	V8 W12 Day 85 ±5 days	V9 W16 D113 ±5 days	V10 W18 Day 126 ±7 days		
	EFFICACY/ PATIENTS REPORTED OUTCOMES											
	NRS (g)	•	Once daily by the subject at home in the evening until Day 126									•
VRS (g)			Once daily by the subject at home in the evening until Day 126									•
Sleep disturbance NRS (h)			Once daily by the subject at home in the morning until Day 29									
DPS (i)			•			•						
DLQI			•			•			•			•
Prurigo Assessment Scale (PAS)			•			•		•	•		•	•
IGA			•			•		•	•		•	•
PK AND ADA ASSESSMENTS												
Blood sample for PK			•	•	•	•	•	•	•	•	•	•
Blood sample for ADA			•		•	•	•	•	•	•	•	•
PHARMACODYNAMIC ASSESSMENTS												
Blood sample for biomarkers			•			•			•			
D-Squares samples			•			•			•			
4-mm skin biopsies (j)			•					•				
Control of biopsies healing (k)				•					•			
BIOPHYSICAL ASSESSMENTS												
Photos of whole body (l)			•			•		•	•		•	
Actigraphy			Every day until Day 29									
Exit Form											•	

(g) NRS and VRS must be performed by the subject at home using the device provided by the site once daily in the evening from screening 2 to the last visit.  
 (h) NRS for sleep disturbance must be performed by the subject at home using the device provided by the site once daily in the morning from screening 2 to Day 29.  
 (i) DPS must be performed by the subject at home following instruction provided by the Nurse on site and then subject should record DPS 24, 48 & 72 hrs after the 1st injection and at week 4 before the injection.  

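### The fixed Week 18 diary window makes the itch score missing for fully compliant subjects whose permitted final visit falls on Days 119–124, and it does not match the SAP's own window rule

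*SAP*

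**What the plan says.** SAP 5.2 (Analysis Visit) says that diary data are classified "during the 7 days prior to the target day of analysis visit". It then lists the windows, among them "Day 106 to 112 = Week 16" and "Day 120 to 126 = Week 18". The visit table in the same section gives target days of 113 for Week 16 and 126 for Week 18.

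SAP 4.2.1.1 says that the subject "will complete the assessment once daily at home in the evening throughout the clinical trial". It also sets the minimum: "If a subject has less than 5 diary entries in a week, the weekly average scores will be set to missing". SAP 4.2.1.2 applies the same minimum to the VRS. The footnote to the SAP's schedule of assessments (Appendix 1) has both scales recorded "once daily in the evening from screening 2 to the last visit".

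In Protocol 8.1.3.2 the heading for the final visit begins "Visit 10 / Day 126, Week 18 (+/- 7 days", and one of the tasks at that visit is: "Collect the device used for Pruritus assessments". The SAP's schedule also shows Day 126 ± 7 days.

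SAP 5.7.3.1 analyses change in NRS and VRS at Weeks 1, 2, 4, 8, 12, 16 and 18. SAP 5.7.1.3 makes LOCF the main imputation method, with observed-case and multiple-imputation analyses beside it.

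**The concern.** There are two separate points. First, the stated rule and the listed window disagree for Week 18 by one day, so two programmers working from the same section could derive different scores.

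Second, and more important, the pruritus diary continues past every earlier scheduled visit, so the date of the visit does not shorten those windows. At Visit 10 the diary stops. An early but permitted final visit therefore cuts into the Week 18 window, and the subject can fall below five entries without having missed one.

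What is at stake is the last follow-up time point for itch. Protocol 3.1 places the end of follow-up 10 weeks, or five half-lives, after the last injection. If LOCF fills the gap with Week 16, the value comes from 14 days earlier, about one half-life given the two weeks in Protocol 1.3. A return of itch between Weeks 16 and 18 could then be hidden for these subjects.

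**Working it through.** **1. Rule against list.** For target day T the rule gives Days T−7 to T−1.

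| Visit | T | Rule | Listed | Agree |
|---|---|---|---|---|
| Week 1 | 8 | 1–7 | 1–7 | yes |
| Week 2 | 15 | 8–14 | 8–14 | yes |
| Week 4 | 29 | 22–28 | 22–28 | yes |
| Week 8 | 57 | 50–56 | 50–56 | yes |
| Week 12 | 85 | 78–84 | 78–84 | yes |
| Week 16 | 113 | 106–112 | 106–112 | yes |
| Week 18 | 126 | 119–125 | 120–126 | no |

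The listed Week 18 window would follow from a target of Day 127 (120 = 127 − 7), or from a rule of T−6 to T that no other visit uses.

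**2. Entries available at Week 18.** Inputs: permitted visit day V from 126 − 7 = 119 to 126 + 7 = 133, which is 15 days; window 120–126; minimum five entries. Because entries are made at home in the evening and the device is collected at the visit, the last entry is taken as Day V−1. The greatest possible number of entries is max(0, min(126, V−1) − 120 + 1).

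| V | 119 | 120 | 121 | 122 | 123 | 124 | 125 | 126 | 127–133 |
|---|---|---|---|---|---|---|---|---|---|
| Maximum entries | 0 | 0 | 1 | 2 | 3 | 4 | 5 | 6 | 7 |

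Visits on Days 119–124 cannot reach five: 6 of 15 permitted days. A Day 125 visit allows no missed evening and an on-target Day 126 visit allows one; a full window allows two.

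**3. Variants.**
- Entry still made on the visit day, window 120–126: Days 119–123 fail, 5 of 15.
- Window moved to 119–125, last entry on V−1: Days 119–123 fail, 5 of 15.
- Both changes: Days 119–122 fail, 4 of 15.

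Correcting the one-day mismatch alone therefore rescues only Day 124 visits.

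**4. Share of subjects.** The documents give no distribution of visit days, so these are assumptions. Uniform over the 15 days: 6/15 = 40%. Normal, with P(V ≤ 124) = Φ((124.5 − centre)/SD):

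| Centre | SD 2 | SD 3 |
|---|---|---|
| Day 126 | Φ(−0.75) = 23% | Φ(−0.50) = 31% |
| Day 127 | Φ(−1.25) = 11% | Φ(−0.83) = 20% |

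Day 127 is a plausible centre because the final visit is also described as 10 weeks after the last injection, and 57 + 70 = 127.

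**5. What replaces the missing score.** The usual LOCF donor is Week 16, Days 106–112, and 120 − 106 = 14 days.

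**The case against.** The strongest reply has four parts.

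- **The listed windows are regular.** Each runs from Day 7k−6 to Day 7k for week k, and Days 120–126 are study week 18. What is irregular is the target of Day 126, since every other target is 7k+1. This stands: the mismatch can be settled in the wording as well as in the window, and by itself it is nearly immaterial.
- **Few subjects may come that early.** A site that counts 10 weeks from an on-time Week 8 injection (Day 57 ± 2) would see the subject on Days 125–129, where five entries are possible. This is fair, and it is why no single percentage should be quoted. But the protocol permits Days 119–133, and the analysis rule should cover what is permitted.
- **The schedule table says that NRS and VRS run until Day 126.** That does not help a subject who has already returned the device.
- **A fixed window keeps the time point comparable.** This also stands. Tying every subject's Week 18 score to the actual visit would move the averaging week by up to 14 days between subjects (Days 112–118 for a Day 119 visit, 126–132 for a Day 133 visit) and would use Day 112 in both Week 16 and Week 18.

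A reader might also infer that Week 18 is the only off-treatment itch measurement. It is not. Week 16 is a follow-up visit too, eight weeks after the last injection, and NRS and VRS are analysed there.

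**Conclusion.** The point holds for one late secondary time point. As written, the SAP leaves Week 18 NRS and VRS missing for fully compliant subjects seen on Days 119–124, or Days 119–123 if an entry is made on the visit day. LOCF then usually carries Week 16 forward, and the observed-case analysis omits them. The cause is the combination of a fixed window, a ± 7-day final visit, device return at that visit and the five-entry minimum; the one-day mismatch accounts only for Day 124.

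The size is 6 of 15 permitted visit days. The proportion of subjects is unknown: about 11–31% under the normal assumptions above and 40% if visits were uniform.

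Some stronger inferences are not supported. The primary endpoint is not touched, because its window (Days 22–28) follows the rule and the diary continues past that visit. Nothing in the documents suggests that loss would differ by arm, since visits are scheduled under blinding. The cost is therefore lost or displaced information at Week 18, not a demonstrated bias in the treatment comparison.

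The day counts assume a first dose on the day of randomization. The LOCF donor is Week 16 only if that week was scored and no rescue was used before it. Device collection is taken from the supplied protocol (V00), whereas the SAP cites Amendment Version 2.0; the SAP's own schedule keeps Day 126 ± 7 days and diary entry up to the last visit.

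**What to change.** In SAP 5.2, before unblinding:

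1. Make the stated rule and the listed Week 18 window agree, by changing either the wording or the days.
2. Keep the fixed window for every subject with at least five entries in it.
3. For a subject left with fewer than five because Visit 10 took place early within Days 119–133 and closed the diary, use the last seven diary days before Visit 10, counting only days after the Week 16 window (Day 113 onward), with the same five-entry minimum. Apply this to NRS and VRS alike.

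A Day 119 visit then has six usable days (113–118), and visits on Days 120–124 have seven, so a fully compliant subject can be scored on every permitted visit day and no day is counted twice.

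The cost is a line or two of SAP text and the matching programming; no new data are needed. The downside is that for these subjects the averaging week lies earlier than the nominal one: by 3 days for a Day 124 visit (117–123 against 120–126) and by up to about 8 days at its end for a Day 119 visit (118 against 126). That is closer to Week 18 than the Week 16 value that LOCF would otherwise supply. Reporting how many subjects used the fallback, by arm, would let readers judge its effect.

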Efficacy results were also obtained in this phase 1 study with 36 moderate-to-severe Japanese AD subjects receiving a single dose of nemolizumab (0.3mg/kg, 1mg/kg or 3mg/kg) or placebo with concomitant topical hydrocortisone butyrate. Intensity of pruritus decreased as early as week 1 in the nemolizumab groups, by a similar degree with all three doses. Treatment with nemolizumab also increased sleep efficiency as measured by actigraphy and decreased the use of TCS in the study. Incidence of AE in AD subjects was similar between nemolizumab groups and placebo group, and was not dose-dependent. The most common AEs reported with nemolizumab included aggravated atopic dermatitis, folliculitis and nasopharyngitis. One subject in the group of 3 mg/kg was diagnosed with asthma: the subject experienced some degree of breathlessness from day 9 after nemolizumab administration and symptoms had resolved by day 22. The subject experienced no further respiratory symptoms until the last observation.

In the completed phase 2a study, the safety, tolerability and efficacy of nemolizumab monotherapy were evaluated in 264 moderate-to-severe AD subjects who were inadequately controlled by or intolerant to topical therapy (CIM003JG). The study included a 12-week randomized, double-blind, placebo-controlled period (Part A), a 52-week extension (Part B), and a 12-week follow-up period without treatment. At week 12, all doses of nemolizumab (0.1mg/kg, 0.5mg/kg or 2.0mg/kg) administered subcutaneously every 4 weeks (Q4W) were statistically significantly more effective than placebo in reducing pruritus visual analogue scale (VAS), with 0.5mg/kg and 2.0mg/kg doses being more effective than 0.1mg/kg. No additional benefit was observed with the 2mg/kg Q4W or Q8W compared with 0.5mg/kg Q4W. The mean percent changes in Eczema Area and Severity Index (EASI), Body Surface Area (BSA) of AD, SCORing Atopic Dermatitis (SCORAD), Investigator's Global Assessment (IGA) and sleep disturbance VAS were also numerically greater in all treatment groups than in the placebo group. The greatest improvements were generally observed in the nemolizumab 0.5 mg/kg and 2.0 mg/kg Q4W groups. Subjects who received placebo in Part A were randomized to receive 0.1mg/kg, 0.5mg/kg or 2.0mg/kg Q4W in Part B. There was evidence of a progressive improvement in all efficacy parameters with prolonged treatment.

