#### 4.2.3.2 Physical examination and vital signs

**Physical examination:** The physical examination will be performed at screening 1, baseline, weeks 4, 8, 12, 18, or early termination and/or unscheduled visits when applicable.

All clinically significant abnormal findings at the screening visit will be recorded in the Medical History form. Any clinically significant changes from the screening visit will be recorded as an AE.

**Vital signs:** The vital signs will be evaluated at screening 1, baseline, weeks 1, 2, 4, 8, 12, 16, 18, or early termination and/or unscheduled visits when applicable.

Vital signs will include pulse rate, systolic and diastolic blood pressure (after the subject has been sitting for at least 5 minutes). All abnormal values at the screening visit identified as clinically significant by the investigator will be recorded in the Medical History form. Any clinically significant changes from the screening visit will be recorded as an AE.

**Height and Weight:** Height will be measured at the baseline visit only, and weight will be measured at baseline, weeks 4, 8, and 12.

Any clinically significant weight changes from the screening visit will be recorded as an AE.

Blood pressure (systolic and diastolic), pulse rate, and weight values meeting criteria for potentially clinically significant values (PCSV) will be reported.

Criteria for PCSV for vital signs and weight are listed in Appendix 2.

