##### **5.8.5.2 Peak Expiratory Flow (PEF)**

For subject with medical history of asthma, PEF measurements (absolute values and change from baseline for actual PEF and %predicted PEF) will be summarized by visit and treatment group.

Number and percentage of subjects who met the following criteria will be summarized.

- With %predicted PEF less than 80%
- With  $\geq 20\%$  change (decrease) from baseline in PEF

A by-subject listing of respiratory assessments/PEF will be provided.

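### Read as written, SAP 5.2 usually keeps a low PEF reading from an unscheduled visit out of the two PEF threshold counts in SAP 5.8.5.2

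*SAP*

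**What the plan says.** PEF is measured only in subjects with a history of asthma. It is taken at each visit, including early termination and unscheduled visits (Protocol 7.2.2.4 and 8.1.4).

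SAP 5.8.5.2 summarises PEF values and changes by visit and arm. It then adds: "Number and percentage of subjects who met the following criteria will be summarized". The two criteria are PEF below 80% of predicted and a decrease of at least 20% from baseline. The section does not say which readings feed these counts.

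The Analysis Visit part of SAP 5.2 contains four statements that bear on this:

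- Slotting: "Assessments at early termination and unscheduled visits will be slotted based on the following visit window".
- Scheduled visits: non-diary data, including "respiratory assessment/PEF, will be analyzed according to actual scheduled visits".
- Selection, for efficacy data and for safety data other than laboratory tests: "where two or more assessments (include both scheduled and unscheduled assessments) are available for the same visit interval", then "the one closest to the target visit date will be used for the summary and analyses".
- Exemption: "All post baseline assessments, including repeated or unscheduled visits, will be used for potentially clinically significant value (PCSV) determinations".

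PCSV criteria exist for vital signs and weight (SAP 4.2.3.2: "Blood pressure (systolic and diastolic), pulse rate, and weight values meeting criteria for potentially clinically significant values (PCSV) will be reported"; limits in Appendix 2) and for laboratory tests (SAP 5.8.4 and Appendix 5). PEF appears in neither appendix, and 5.8.5.2 does not call its criteria PCSVs.

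**The concern.** Closeness to the target day is a reasonable way to choose one value for a by-visit mean. It is a poor way to decide whether a subject ever crossed a safety threshold, because it ignores how low the reading was. Unscheduled visits are where a symptomatic reading is most likely, and the rule favours the routine reading over it. A low blood pressure at an unscheduled visit counts towards its PCSV table, but a 20% PEF fall recorded at the same visit may not count towards the PEF table.

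This matters because asthma is listed as an important potential risk (Protocol 1.4) and is the AESI with 24-hour reporting (Protocol 7.2.4.2.3). The protocol itself uses a 20% PEF fall as a trigger for referral (7.2.2.4) and 80% of predicted as an exclusion limit (5.4, item 11). If a subject's only low reading came from an unscheduled visit, the by-arm count could record no event for that subject although the reading is in the database.

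Scheduled visits are four weeks apart from Week 4 to Week 16, so there is room for such readings. Protocol 1.2 gives one example of timing: "the subject experienced some degree of breathlessness from day 9 after nemolizumab administration and symptoms had resolved by day 22".

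**Working it through.** The plan states no figure to reproduce. The check asks on which days an unscheduled PEF would lose to an attended scheduled visit.

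**Inputs.** Target days and day ranges are from the Analysis Visit table in SAP 5.2. Allowed visit deviations are from the schedule of assessments (Protocol Table 2). Injections 2 and 3 are due on Days 29 and 57.

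**Rule.** For a reading on day d in an interval with target T and allowed deviation w, the distance is |d − T|. If |d − T| > w, the reading loses whichever in-window day the scheduled visit took place.

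**Example: 9 to 22 days after an injection given on its target day.**

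| Injection | Days | Interval (target, w) | Distance to target | Certain to lose |
|---|---|---|---|---|
| 2 (Day 29) | 38–43 | Week 4 (29, 2) | 9 to 14 | 6 of 6 |
| 2 (Day 29) | 44–51 | Week 8 (57, 2) | 13 down to 6 | 8 of 8 |
| 3 (Day 57) | 66–71 | Week 8 (57, 2) | 9 to 14 | 6 of 6 |
| 3 (Day 57) | 72–79 | Week 12 (85, 5) | 13 down to 6 | 8 of 8 |

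That is 14 of 14 days after each injection. If the injection moves by the allowed 2 days either way, the result is unchanged for injection 2 and for injection 3 given early. For injection 3 given on Day 59, the span is Days 68–81. Day 80 is 5 days from target, which ties with a visit at the window edge, and Day 81 is 4 days away. At most 2 of 14 readings could be kept.

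**After injection 1** (Day 1), the same span is Days 10–23. The Week 2 visit, Day 15 ± 2, falls inside it and includes PEF.

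**All intervals.** Days certain to lose even if the scheduled visit was at the edge of its window:

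| Interval | Day range | Target ± w | Days certain to lose |
|---|---|---|---|
| Week 1 | 2–11 | 8 ± 1 | 7 of 10 |
| Week 2 | 12–22 | 15 ± 2 | 6 of 11 |
| Week 4 | 23–43 | 29 ± 2 | 16 of 21 |
| Week 8 | 44–71 | 57 ± 2 | 23 of 28 |
| Week 12 | 72–99 | 85 ± 5 | 17 of 28 |
| Week 16 | 100–119 | 113 ± 5 | 9 of 20 |
| Week 18 | 120–133 (assumed end) | 126 ± 7 | 0 of 14 |

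The total is 78/132 = 59%. For Weeks 4 to 16 it is (16 + 23 + 17 + 9)/(21 + 28 + 28 + 20) = 65/97 = 67%. If every scheduled visit fell exactly on target, the loss would be every day but the target day: (132 − 7)/132 = 125/132 = 95%. These are shares of calendar days, not probabilities that a reading is lost.

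**The sentences together.** The counts above apply the slotting and selection sentences. The scheduled-visits sentence, taken alone, would leave out every unscheduled PEF, even the only one in its interval. The two readings conflict, and neither guarantees that a low unscheduled value is counted.

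**The case against.** The strongest reply is that exclusion from the counts is inferred. In 5.8.5.2 the by-visit wording belongs to the values and changes, and the sentence on the two criteria has no such limit. These are threshold criteria, and 5.2 already uses all readings for threshold criteria of the PCSV kind, so the sponsor may intend the same for PEF. That intention is possible but not written. The general rule covers non-laboratory safety data, the exemption names PCSVs, and PEF is not among them. A programmer following the text would apply the general rule.

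Three stronger readings are tempting, and the documents support none of them.

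- *That asthma episodes would be missed.* New or worsening asthma is an AESI at whatever visit it is found (SAP 4.2.3.3), and AESIs are summarised and listed (SAP 5.8.3). PEF has a by-subject listing with no stated exclusion. These are real safeguards, but they do not replace the counts: a PEF fall is not itself an AESI, and a listing is not a comparison between arms.
- *That unscheduled readings are always dropped.* Under the slotting and selection sentences, one is kept if it is closest to target or alone in its interval, for example after a missed visit.
- *That the case in Protocol 1.2 shows what would be lost.* That subject was diagnosed with asthma after a single 3 mg/kg dose, and no earlier asthma is stated. A new diagnosis here, in a subject without an asthma history, would have no PEF under any rule. The same timing after injection 1 takes in the Week 2 visit. The case serves only to illustrate timing.

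**Conclusion.** The point holds for the two PEF threshold counts and for nothing wider. Under SAP 5.2 as written, those counts usually leave out a low PEF from an unscheduled visit when the scheduled visit in the same interval was attended. After injections 2 and 3 on their target days, this is so on all 14 days of the 9-to-22-day span. Over Weeks 4 to 16 it is certain on at least 65 of 97 days.

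These figures assume that the scheduled visit took place within its window with PEF recorded, and that slotting and closest-to-target selection apply. If the scheduled-visits sentence governs instead, the exclusion is complete.

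The effect on the counts themselves cannot be computed. The documents give neither the number of subjects with an asthma history among the roughly 70 to be randomised nor a rate of unscheduled visits. It could be nil if no such subject has a low off-schedule reading. The correction is still worth making, because the error can only hide recorded low readings and the SAP already has the right rule for comparable safety thresholds.

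**What to change.** In SAP 5.8.5.2, state that both PEF criteria are evaluated per subject on every post-baseline PEF, including unscheduled and early termination readings, as 5.2 does for PCSVs. Count each subject once per criterion, with subjects who have an asthma history as the denominator.

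In SAP 5.2, keep closest-to-target selection for by-visit PEF summaries only. Reconcile the sentence that assigns PEF to actual scheduled visits with the one that slots unscheduled assessments.

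The cost is a few lines of SAP text and minor programming. The readings are already collected, and neither visits nor clinical management change.
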